**Monitoring subjects and criteria for withdrawal of subjects from study:**

The types, frequency, and duration of tests and visits are outlined on the flow diagrams at the end of this protocol document (Appendices B and C). Subjects will be examined at each of the two visits, which will be completed within a 2 month time period. If unanticipated toxicities are uncovered during the study, we will report these promptly to the IRB and FDA.

Subjects will be informed that they may withdraw from the study at any time.

Noncompliance with study procedures may lead to withdrawal of study subjects. Other events that will result in discontinuation of treatment include:

1. Inability to tolerate drug secondary to perceived or observed side effects.
2. Pregnancy.
3. Any verified abnormalities in laboratory values or physical status that cannot be explained by an intercurrent unrelated illness (or by obesity and insulin resistance itself)

that are considered WHO grade 2 or greater for gastrointestinal, hematologic, clinical hemorrhage, kidney/bladder, alopecia, pulmonary, cardiac, neurocerebellar, allergy, flu-like symptoms, metabolic, or eye toxicities; and grade 3 or greater for infection, anorexia, circulatory, neurologic, dermatologic, coagulation, endocrine, or performance status toxicities.

**Adverse event reporting:**

Adverse events, protocol deviations, unanticipated problems (UP), Unanticipated Adverse Device Effects (UADEs), serious adverse events, sponsor and serious, are defined as described in NIH HRPP SOP 16 (“Reporting Requirements for Unanticipated Problems, Adverse Events and Protocol Deviations.”). All adverse events occurring during the study, including those observed by or reported to the research team, will be recorded. Serious unanticipated problems, and serious protocol deviations, will be reported to the IRB and CD as soon as possible but not more than 7 days after the PI first learns of the event. Not serious unanticipated problems will be reported to the IRB and CD as soon as possible but not more than 14 days after the PI first learns of the event. Not serious protocol deviations will be reported to the IRB as soon as possible but not more than 14 days after the PI first learns of the event.

Deaths will be reported to the Clinical Director within 7 days after the PI first learns of the event.

The PI will immediately report SAEs to the Sponsor according to the requirements of 21 CFR 312.64(b) and as agreed upon with the sponsor. The PI will record nonserious AEs and report them to the Sponsor according to the timetable for reporting specified in the protocol (21 CFR 312.64(b)).

A post test questionnaire will be administered after the inpatient admission in the main study, and the questionnaire will also be administered every hour from 6am to Noon during the inpatient

admission in the dose-establishing study. A sample questionnaire is attached to the end of this document as Appendix D.

**Waiver of Reporting to the IRB of anticipated minor protocol deviations, adverse events and deaths due to underlying disease or population under study unless determined to be an Unanticipated Problem**

- For waiver of Reporting to the IRB of anticipated minor protocol deviations

The following anticipated minor deviations in the conduct of the protocol will not be reported to the IRB unless they occur at a rate greater than that which is anticipated to occur:

Problem	Expected Frequency
Rescheduled appointment for protocol visit	50%
Inability to obtain intravenous access after 2 attempts	25%
Venous sample at a time point not obtained	25%
Hemolysis or other issue preventing analysis of a blood or urine sample	25%
A research subject was enrolled but did not meet eligibility criteria	5%
A research subject met withdrawal criteria but was not withdrawn	5%
Subject had to make an additional visit for lab work (e.g. arrived too late for bloodwork, specimen result hemolyzed/equivocal, etc.)	30%
Inadvertent loss of samples or data	10%
Inadvertent collection of additional noninvasive data (e.g. extra survey)	5%
Appointment conducted >2 weeks beyond anticipated date	10%

Participant did not take all medication doses as prescribed	10%
Lost medication	5%

If the rate of these events exceeds the rate specified by the protocol, the events will be classified and reported as though they are Unanticipated Problems.

- **For waiver of Reporting to the IRB of anticipated adverse events:**

The following anticipated non-UP adverse events will not be reported to the IRB unless they occur at a rate greater than that known to occur in this population:

Problem	Expected Frequency
Pain during intravenous catheter insertion	60%
Bruising, fainting or lightheadedness after a blood draw	20%
Red or white skin reaction to ELA Max numbing cream	100%
Phlebitis after intravenous catheter	20% (1 subject)
Occurrence of adverse response to niacin administration	See Table 2 for time point based frequencies

- ***For waiver of Reporting to the IRB of anticipated adverse events on an FDA-regulated trial:***

The following anticipated adverse events will not be reported to the IRB unless they occur at a rate or severity greater than that known to be associated with Niacin. Examples of expected adverse events include but are not limited to those events detailed in the FDA-approved package insert for niacin and in the protocol’s risk section. The waivers that apply here are:

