at 9:30am. A dose of niacin (dose determine in the dose-establishing study) or placebo will be administered by mouth at 7:30am, 8:30am, 9:30am, and 10:30am . The study will be repeated the next day in the same fashion. The order of niacin 500 mg or placebo will be randomized. Blood will be sampled from an indwelling intravenous line at times -60, -30, 0, +30, +45, +60 minutes of arginine infusion for measurements of GH, free fatty acids, glucose (via bedside glucometer), and insulin concentrations. Blood will also be sampled at times -30, 0, +30, +45, +60, +75, +90, and +120 minutes of L-dopa administration for the same serum concentrations. GHRH and Somatostatin will be sampled hourly at 7:30am, 8:30am, 9:30am, 10:30am, and 11:30am, with two additional measurements at +30 minutes (9am) of arginine infusion and +30 minutes (10am) of L-dopa administration. After completion of this sampling, the subject will be given an ad lib diet.

7. **Discharge:** Subjects will be discharged following the growth hormone stimulation test on the second day.

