**Table 2: Time Point Based Expected Adverse Reactions During Niacin Administration**

	Time (hours after Niacin administration)
--	---

Expected adverse reactions (%)	1	2	3	4	5	6
Headache	20	0	0	0	0	0
Flushing	100	100	100	50	50	0
Feeling warm	100	100	100	60	20	0
Nausea	20	20	0	0	0	0
Vomiting	20	20	0	0	0	0
Stomach Ache	20	20	0	0	0	0
Diarrhea	20	0	0	0	0	0
Tingling	20	20	0	0	0	0
Light-headedness	20	0	0	0	0	0
Itchiness	100	100	60	40	0	0
Rashes	20	20	20	20	0	0

If the rate or severity of these events exceeds the rate or severity anticipated in the protocol or FDA-approved package insert, the events will be classified and reported as though they are Unanticipated Problems.

Because we anticipate that other mild symptoms may occur in the course of participation in the protocol that are unrelated to study drug or participation, we will not submit Unanticipated Problems for mild signs/symptoms (CTCAE Grade  $\leq 2$ ), such as rhinorrhea, nasal congestion, watery eyes, cough, lightheadedness, fever blister, etc., that occur infrequently ( $\leq 10\%$ ). Such events will be reported at the time of the IRB Annual Review.

**Data safety monitoring board (DSMB):** A DSMB will be assembled for oversight of this protocol by the Clinical Director, NICHD, with membership and scope determined by applicable institutional guidelines. The DSMB will meet to evaluate all serious adverse events and will at a minimum convene yearly. The DSMB will examine whether there is evidence of safety for niacin administration. The DSMB will review adverse event questionnaire data, and reports of side effects from all visits. These reports will also be supplemented by a manual review by the investigators, who will add any other events not captured by these systems. Results will be presented as an A vs. B analysis prepared by the data manager. The DSMB will be asked to prepare a detailed report to

supply to the IRB that describes any adverse events discussed, and that explains the DSMB's vote to allow the study to continue or recommendation to end the study.

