### **Randomization**

For randomizing order of administration of niacin and placebo, investigators will assign consecutive code numbers to participants from prespecified lists stratified by group, sex, and BMI (95-99th percentile or >99th percentile). The NIH Clinical Center Investigational Drug Management and Research Section will use permuted blocks with stratification to generate the allocations that translate code numbers into study group assignments by using a pseudo-random number program. Pharmacy personnel not otherwise involved with the conduct of the study will dispense study capsules in containers that appear identical and differ only by participant code number. No participant, investigator, or other medical or nursing staff interacting with participants will be aware of study group assignments during the trial.

Arginine hydrochloride 10% solution is approved by the FDA for growth hormone testing. This agent is available through the NIH pharmacy and is on the formulary. It will be used at a dose of 500 mg/kg IV up to maximum of 30g infused over 30 min on two consecutive days. This dosing corresponds to 5 mL/kg, with a maximum dose of 300 mL on two consecutive days.

L-dopa is not approved by the FDA for growth hormone testing, but is approved for other uses. L-dopa has been used clinically for many years for the purpose of growth hormone testing. L-dopa powder will be obtained from Spectrum Chemicals, which has supplied us with a Certificate of GMP. From 2011-2016, L-dopa was packaged, supplied, and distributed to the inpatient staff by the NIH pharmaceutical development section as 250 mg capsules. The analytical group of

Pharmaceutical Development Service conducted testing according to USP standards for medications used in this protocol prior to release for human consumption. Starting in mid-2017, Pine Pharmaceuticals will compound the 250 mg capsules and perform bioburden testing per the United States Pharmacopeia (USP) <61> and <62> standards. Purity and stability testing will be performed by the NIH Investigational Drug Management and Research Section, which will track and dispense all medications to the inpatient staff.

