## Appendix D

### Post-Test Questionnaire

To be administered hourly from 6am-Noon during the inpatient stay of the dose-establishing study and at the end of the inpatient stay of the main study

Please check off the symptoms that the patient experienced during the time the patient as staying at the NIH. Then indicate how long it lasted and how severe it was.

Symptom	Present?	Duration	Severity (please choose one)		
			1 (mild)	2 (moderate)	3 (severe)
Headache					
Flushing of face					
Feeling warm					
Nausea (feeling like vomiting)					
Vomiting					
Stomach ache					
Diarrhea or loose stools					
Tingling in arms or legs					
Light-headed or faint					
Itchiness					
Rash or skin problems					
Other (please list):					

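### One end-of-stay symptom form covers both the niacin and the placebo day, so it cannot show which treatment a symptom followed

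*Combined protocol and SAP*

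**What the plan says.** The main study is a two-day crossover within one admission. Under Main Study: Inpatient evaluation, arginine and L-dopa are given on the first test day with four doses of niacin or placebo, and "The study will be repeated the next day in the same fashion" with the other treatment. The order is randomized, and discharge follows the second test.

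On symptoms, the Adverse event reporting section states: "A post test questionnaire will be administered after the inpatient admission in the main study". The header of Appendix D agrees, placing the form "at the end of the inpatient stay of the main study". The form asks for "symptoms that the patient experienced during the time the patient as staying at the NIH". It names 11 symptoms plus a free-text row, with fields for presence, duration and severity. In the dose-establishing studies the same form was scheduled hourly.

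On use of the data, the DSMB paragraph says "The DSMB will examine whether there is evidence of safety for niacin administration" and "The DSMB will review adverse event questionnaire data, and reports of side effects from all visits". It adds: "Results will be presented as an A vs. B analysis prepared by the data manager". A and B are not defined. The first item under Specific Hypotheses includes a clause that niacin will not cause significant adverse effects.

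**The concern.** A crossover can compare niacin and placebo within the same child, but only if each observation is tied to a day. Here the symptom form pools both days. Symptom type cannot fill the gap, because both stimulants are given on both days and share side effects with niacin. A DSMB looking at a count of nausea or vomiting from this form could not tell how much came from niacin and how much from the stimulation test itself. What is at stake is the placebo-controlled part of the safety evidence in children.

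**Working it through.** **1. What one form covers.** Appendix C gives admission by 4:00 PM and the end of Day 2 testing at 11:30am. From 4:00 PM on the admission day to 4:00 PM on Day 1 is 24 h, and from there to 11:30am on Day 2 is 19.5 h. The form therefore covers at least 24 + 19.5 = 43.5 h. Day 1 testing also ends at 11:30am, so Day 1 symptoms are recalled about 24 h later. By contrast, symptoms are tabulated at 7 hourly readings for one test in dose-establishing study 1 (hours 0 to 6) and at 5 in study 2 (hours 0 to 4).

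**2. What the form can identify.** Let s be the proportion ticking a symptom, and pN and pP the niacin-day and placebo-day proportions. Leaving aside symptoms outside the two test sessions,

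max(pN, pP) ≤ s ≤ min(1, pN + pP).

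From the form alone, pN can be anything from 0 to s, and the difference pN − pP anything from −s to +s. As an illustration with an assumed s = 40%, pN and pP can each lie between 0% and 40% (with a sum of at least 40%), and the difference anywhere from −40 to +40 percentage points. Duration does not help, because it is not onset.

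**3. The A vs. B presentation.** If A and B are the two treatments, this form cannot fill the table. If they are the two treatment orders, the table can be filled; the Randomization section does use group language for orders, with allocations that "translate code numbers into study group assignments". But each order contains one niacin day and one placebo day. If symptom rates depend only on treatment, both orders have the same expected rate on the form whatever niacin adds, so that table would not show niacin's effect.

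**4. Overlap with the stimulants.** From the Risks and Discomforts section:

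| Form symptom | Niacin | Arginine | L-dopa |
|---|---|---|---|
| Headache | listed | listed | listed |
| Flushing | listed | listed | not listed |
| Nausea | listed | listed | listed |
| Vomiting | listed | listed | listed |

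That is 4 of the 11 named symptoms.

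**5. Secondary check: the expected-rate table.** The IRB reporting waiver uses a table of expected reactions at hours 1 to 6 after niacin (11 symptoms × 6 hours = 66 cells). Its header does not say whether the clock starts at the first or the most recent dose, and its source is not stated.

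- Against study 1 (11 × 6 × 2 dose groups = 132 cells), no observed rate exceeds the table. Of the 66 table cells, 57 equal the higher of the two study 1 groups and 9 lie above it; 4 of those 9 equal the study 2 rate.
- Against study 2, which used the main study's hourly regimen (11 × 4 hours = 44 cells, n = 5, so 20% is one child), 7 cells exceed the table on a first-dose clock:

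| Symptom, hour | Study 2 | Table |
|---|---|---|
| Nausea, 2 | 40% | 20% |
| Nausea, 4 | 20% | 0% |
| Vomiting, 4 | 20% | 0% |
| Stomach ache, 1 | 40% | 20% |
| Stomach ache, 3 | 20% | 0% |
| Stomach ache, 4 | 20% | 0% |
| Tingling, 1 | 60% | 20% |

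- Six of the seven exceed by one child and tingling at hour 1 by two. Three (nausea at hour 4, stomach ache at hours 3 and 4) only equal the pre-dose 20%.
- On a most-recent-dose clock (doses at hours 0, 1, 2 and 3, so every reading meets the hour-1 limit), 3 of 44 exceed: nausea at hour 2, stomach ache at hour 1 and tingling at hour 1. The first-dose clock is the likelier reading, since the table runs to hour 6 as study 1 did.

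**The case against.** The form is not the only safety record. All adverse events observed by or reported to staff are to be recorded, investigators add events by manual review, Appendix B lists an Adverse Drug Event Assessment for the main-study admission, and Appendix D is described as a sample. The withdrawal criteria and the provision for intolerable flushing both presuppose bedside observation on the test day, and the DSMC has access to unblinded data. More consequential events would therefore probably be placed by day. This narrows the loss mainly to mild, short-lived symptoms known only from the checklist. It does not remove the loss, because none of these routes is stated to record the test day for checklist symptoms, and the questionnaire is named as DSMB input.

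The safety clause concerns significant effects only, and the Data Analysis section plans no symptom analysis. Hourly niacin data without the stimulants already exist for 2 + 5 + 5 = 12 obese children, 5 of them on the main-study regimen. This is useful background, but those studies had no placebo and no control-group children.

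The overlap is uneven. Flushing or warmth at hour 1 was reported by 80 to 100% on niacin, whereas arginine flushing appears only among reports for a generally well tolerated agent. The practical ambiguity is mainly nausea, vomiting and headache. That stands.

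The expected-rate table is a separate matter and shows no reporting failure. The numbers are small, the trigger also refers to the package insert, and the protocol describes the study 2 events as largely expected. It is a minor point.

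**Conclusion.** The concern holds. Followed as written, the plan yields one form per child spanning both treatments, and that form alone cannot attribute any of the 11 named symptoms to niacin or placebo. It affects every child who undergoes both test days: 40 planned completers, with up to 50 starting. The conclusion is limited to what the form can do. It assumes that no unstated version of the form carries a date, and it does not claim that the trial as a whole cannot attribute adverse events. The plan should be changed because the loss is avoidable and, after discharge, the missing day could be recovered only from memory or from records not stated to hold it. The expected-rate discrepancy leaves unclear which hourly rates count as expected, and the main conclusion does not depend on it.

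**What to change.** Complete Appendix D at the end of testing on Day 1 and again on Day 2, with an added test-day field and an approximate onset hour. Hourly completion is optional. State in the DSMB paragraph that A and B are the two treatments, and supply the within-child table of niacin-day against placebo-day symptoms under that coding. State the clock of the expected-rate table and reconcile its rates with the dose-establishing study 2 results.

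The cost is a few minutes of staff time per test day with the child already on the ward, two extra fields, and a revised table, with no added visits or blood draws. The onset hour would be recalled at the end of a four-hour test and so is approximate; the test day would be exact. A Day 1 form could draw attention to flushing, but the protocol's limitations section already accepts that flushing may reveal the allocation.

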### **Study Design and Methods:**

#### Inclusion Criteria:

Subjects will qualify for the overweight group (for the dose-establishing studies 1 and 2 and main study) if they meet the following criteria:

1. Good general health.
2. Age  $\geq 7$  and  $< 15$  years.
3. Tanner stage I, II, or III for the breast among girls and testes  $< 10$  mL for boys based upon an examination by a trained physician or nurse practitioner.
4. Weight  $> 30$  kg.
5. Fasting plasma glucose  $< 100$  mg/dL, 2 hour post-dextrose glucose  $< 140$  mg/dL, and HgbA1C  $\leq 6.4\%$ .

6. Females who are age 10 or greater must have a negative pregnancy test.
7. Body mass index  $\geq$  95th percentile determined by Centers for Disease Control age and sex specific data (given that most pathology of obesity does not usually emerge until children cross the 95th percentile).
8. No evidence of growth failure as defined as height  $>$  5th percentile.

Subjects will qualify for the non-overweight control group (for the main study only) if they meet the following criteria:

1. Recommended by a pediatric endocrinologist to undergo GH stimulation testing to establish the diagnosis of GH-deficiency.
2. Good general health.
3. Age  $\geq$  7 and  $<$  15 years.
4. Tanner stage I, II, or III for the breast among girls and testes  $<$  10 mL for boys based upon an examination by a trained physician or nurse practitioner.
5. Weight  $>$  30 kg.
6. Fasting plasma glucose  $<$  100 mg/dL, 2 hour post-dextrose glucose  $<$  140 mg/dL, and HgbA1C  $\leq$  6.4%.
7. Females who are age 10 or greater must have a negative pregnancy test.
8. Height  $<$  5th percentile.
9. BMI between the 5th and 85th percentiles determined by Centers for Disease Control age and sex specific data.
10. Birth weight and length not consistent with small for gestational age (SGA) criteria or a history of intrauterine growth restriction (IUGR) based on recall history.

Exclusion criteria (for the dose-establishing studies 1 and 2 and the main study):

Subjects will be excluded if they have any of the following:

1. Baseline creatinine  $\geq$  1.0 mg/dl.

2. Significant cardiac or pulmonary disease likely to or resulting in hypoxia or decreased perfusion.
3. Hepatic disease with elevated liver function tests (ALT or AST)  $\geq 1.5$  the upper limits of normal.
4. Pregnancy.

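### Two deviations that can breach safety criteria are classed in advance as minor and need not be reported to the IRB as deviations until they exceed 5%

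*Combined protocol and SAP*

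**What the plan says.** The general rule and the waiver both stand under Adverse event reporting. The general rule sends serious protocol deviations to the IRB and the Clinical Director within 7 days, and non-serious ones to the IRB within 14 days. The definitions are left to an NIH procedure that the protocol cites but does not reproduce.

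The waiver then introduces a table of anticipated minor deviations which "will not be reported to the IRB unless they occur at a rate greater than that which is anticipated to occur". Most rows are logistical, such as rescheduled visits, missed samples or lost medication. Two are of another kind: "A research subject was enrolled but did not meet eligibility criteria" and "A research subject met withdrawal criteria but was not withdrawn". Each has an expected frequency of 5%. Above the listed rate, events are to be handled as Unanticipated Problems. The heading of the waiver carries an exception, ending "deaths due to underlying disease or population under study unless determined to be an Unanticipated Problem".

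The withdrawal criteria are in the section on monitoring subjects and criteria for withdrawal. Noncompliance may lead to withdrawal. The list that follows is mandatory: "Other events that will result in discontinuation of treatment include" drug intolerance, pregnancy and WHO-graded toxicities. The eligibility criteria include safety items (creatinine, liver tests, significant cardiac or pulmonary disease, pregnancy, glucose tolerance). They also include items of a different nature (height and BMI percentiles, recalled birth size, stimulant use within two years).

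**The concern.** Eligibility and stopping criteria are the main protection for each individual child, and the study is proposed under the regulatory category for research without direct benefit and with only a small increment over minimal risk. The IRB's acceptance of that risk presumes that these criteria are applied. The two rows settle in advance that failing to apply them is minor, whichever criterion was breached, and place that failure beside rescheduled appointments. Read literally, the plan lets a breach of a safety exclusion or a mandatory stop go unreported as a deviation. It also gives no workable rule for when reporting begins.

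**Working it through.** **Step 1: can the 5% be reproduced?** No. It is stated without derivation, so there is nothing to recompute. The candidate denominators come from Determination of Sample Size: 40 completers (20 per group), 50 studied and at most 66 screened. The 50 does reproduce: 40 / (1 − 0.20) = 50.

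**Step 2: events per row that stay waived, if 5% is a final rate.** Reporting starts only above 5%, so the largest waived count is the whole-number part of 0.05 × N.

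| Denominator N | 0.05 × N | Largest waived count | First reportable count |
|---|---|---|---|
| 40 completers | 2.0 | 2 (2/40 = 5.0%) | 3 (7.5%) |
| 50 studied | 2.5 | 2 (2/50 = 4.0%) | 3 (6.0%) |
| 66 screened | 3.3 | 3 (3/66 = 4.5%) | 4 (6.1%) |

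Over the two rows together that is 4 to 6 events.

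**Step 3: if 5% is a running rate instead.** One event gives 1/19 = 5.3% at the 19th child, which is reportable, and 1/20 = 5.0% at the 20th, which is not. A second event stays within the rate only from the 40th child (2/40 = 5.0%). The same breach is then reported or not according to when in enrolment it happens. A third reading is hinted at by the phlebitis row in the companion adverse-event table, which equates 20% with one subject and so implies a denominator of 5. On that base any single event (1/5 = 20%) would be reportable. The documents choose none of these.

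**Step 4: do other channels report the breach?**

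- Monitoring Plan, item 7: serious adverse events go to the safety committee, the IRB and the FDA within 7 or 15 days, and all adverse events go to the IRB and the committee annually. This reports the harm. An ineligible child with no adverse event triggers nothing.
- Data safety monitoring board paragraph: the board reviews serious adverse events, questionnaires and side-effect reports. Deviations are not listed.
- Monitoring Plan, item 4: records of active subjects are checked at least quarterly, but findings go to the IRB only if major and if indicated.
- Exception in the waiver heading: it depends on someone judging an event to be an Unanticipated Problem after the table has called it anticipated and minor.
- Annual catch-up: other mild symptoms that are not submitted as Unanticipated Problems are reported at the IRB's annual review. The deviation table has no matching provision.

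**The case against.** The strongest reply is that a waiver is by nature an exception. It can be read as relaxing only the 14-day rule for non-serious deviations and leaving the 7-day rule for serious ones intact. A reader might infer a flat contradiction with the general rule, and the text does not establish one. What stands is that the order of precedence is unstated, while the rows cover every criterion without distinction.

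A reader might also infer that harm to a child could be hidden. It could not simply be waived away: adverse events and serious adverse events keep their own routes, and unanticipated toxicities go promptly to the IRB and FDA. The gap is confined to the breach as a deviation.

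A third tempting reading is that every event in the withdrawal row means a child kept on study drug after a safety stop, perhaps given niacin again the next day. The row is wider than that, since it can include a noncompliant child whom the team chose to keep. In the crossover each child is assigned niacin on one day only. What remains possible is further exposure within the niacin day, and to arginine and L-dopa, which are given on both days.

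Finally, not all eligibility criteria are safety items, and the arrangement alters reporting, not the criteria themselves. Both points are correct. They support a narrower fix as an alternative, but they do not justify rows that treat all criteria alike.

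**Conclusion.** The point holds in limited form and is worth correcting before the waiver is relied on. As written, the plan classes ineligible enrolment and non-withdrawal as minor in advance, and lets a breach of a safety criterion go unreported to the IRB as a deviation. No other listed channel reliably reports the breach itself.

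The size is 2 or 3 events per row (4 to 6 over both). This assumes that 5% is a final rate on one of the three main-study denominators. These are ceilings under an assumed rule and do not forecast how often breaches will occur. On a running rate the count depends on timing. The conclusion about the text needs none of these assumptions. The documents do not support saying that harm would go unreported, or that the 7-day rule is overridden.

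**What to change.** Remove the two rows, on ineligible enrolment and on non-withdrawal, from the waiver table, so that each event is reported individually under the existing 7-day or 14-day rule. If the sponsor prefers to keep them, the minimum is to:

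- exclude from both rows any breach of a safety eligibility criterion or a mandatory discontinuation criterion;
- state that the rule for serious deviations prevails over the waiver;
- define the denominator of the rate and when it is assessed.

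The logistical rows can stay. Copying these reports to the DSMB is optional. The cost is a small wording amendment and probably a few additional IRB reports over the trial. No stopping rule, eligibility criterion or sample size changes.
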